3.1. The Full Analysis Set (FAS)

FAS includes all randomized subjects. Efficacy analyses will be based on the treatment allocated by the IWRS at randomization (as randomized).

The modified full analysis set (mFAS) includes all FAS subjects who undergo bi-weekly in-clinic up-dosing as described/specified in the protocol and undergo the post up-dosing DBPCFC at Visit 16/Week 28 (a window of -7/+30 days).

The mFAS will be considered as primary analysis set for all efficacy endpoints. The FAS will also be done for all efficacy endpoints as supportive analyses.

FAS-maintenance is a subset of FAS and includes subjects in the FAS who achieve 300 mg/day AR101 for at least 2 weeks in the up-dosing phase and re-randomized based on the treatment allocated by the IWRS at visit 16. The FAS-maintenance is the primary analysis set for efficacy analyses at visit 22.

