5.6.1. Analysis of Primary Efficacy Variable

This primary endpoint will be analyzed using the Cochran-Mantel-Haenszel (CMH) test adjusted by randomization stratification factors (screening peanut-specific IgE level [\leq 100 kUA/L or >100 kUA/L] and baseline body weight [<30 kg, \geq 30 kg and <60 kg, or \geq 60 kg]) to assess the treatment difference in the proportion of responders (i.e., those who "pass" a post up-dosing DBPCFC with 2044 mg [cumulative] peanut protein at visit 16 [Week 28 with a visit window of -7/+30 days]) in the mFAS.- Estimate of treatment difference, p-value, and the 2-sided 95% confidence interval using CMH test will be provided. The number and percent of subjects at each dose level for highest tolerated peanut protein dose at post up-dosing DBPCFC will also be summarized.

The primary estimand of interest for the primary endpoint is described as follows, based on intercurrent event(s) strategy and missing data handling methods:

- The treatment policy strategy will be implemented for the intercurrent event of the treatment discontinuation. The data collected after the patient discontinued treatment will be included in the analysis.
- Missing data for post up-dosing DBPCFC at visit 16 will be handled according to the reason for missingness as follows:
 - If a subject misses the post up-dosing DBPCFC at visit 16 due to COVID-19, the missing data will be imputed by multiple imputation (MI) method for 10 times utilizing available post up-dosing DBPCFC data at visit 16. The MI will utilize logistic regression method with treatment group and randomization stratification.
 - If a subject does not have available DBPCFC data with peanut protein at visit 16 due to reasons not related to COVID-19, this subject will be considered as a nonresponder at visit 16.

Each of complete datasets after the above steps will be analyzed by the CMH test. The SAS MIANALYZE procedure will then be used to generate valid statistical inferences by combining results using Rubin's formula (Rubin, 1987).

Sensitivity analyses will include an analysis of the subset of subjects with available visit 16 DBPCFC data with peanut protein.

The supportive analyses based on FAS and PPS will be performed using primary analysis method.

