5.6.2. Analysis of Secondary Efficacy Variables

Continuous Endpoints at visit 16

Change in the cumulative tolerated dose (log transformed) of peanut protein during a DBPCFC from baseline at visit 16 will be analyzed using analysis of covariance (ANCOVA) with treatment as the main effect, stratification variables and baseline tolerated cumulative amount of peanut protein DBPCFC (log transformed) as covariates. If subjects do not tolerate any dose level, they will be assigned a cumulative tolerated dose of 1 mg prior to converting to the log scale. The least-squares (LS) mean for each treatment group with its corresponding standard error (SE), the LS mean difference between treatment group and its corresponding SE and 95% CI, and the p-value corresponding to the between-treatment-group difference will be reported. In addition, change the

CONFIDENTIAL

Page 40 of 86

cumulative tolerated dose of peanut protein during a DBPCFC at visit 16 will be based on a non-parametric analysis using the van Elteren test.

Missing data for post up-dosing DBPCFC at visit 16 will be handled according to the reason for missingness as follows:

- If a subject misses the post up-dosing DBPCFC at visit 16 due to COVID-19, the missing data will be imputed by MI method for 10 times utilizing available post up-dosing DBPCFC data at visit 16. The MI will utilize regression method with treatment group, randomization stratification, and baseline tolerated cumulative amount of peanut protein DBPCFC (log transformed).
- If a subject does not have an available DBPCFC at visit 16 due to reasons not related to COVID-19, the baseline value at screening DBPCFC will be used to impute the missing post up-dosing DBPCFC data at visit 16.

Each of the complete datasets after the above steps will be analyzed by the ANCOVA. The SAS MIANALYZE procedure will then be used to generate valid statistical inferences by combining results.

Two sensitivity analyses will be performed as below to assess the robustness of results:

- Completed cases will be conducted regardless the rescue medication used.
- MI method: the missing data will be imputed by MI method utilizing available post updosing DBPCFC data at visit 16. The MI will utilize the same regression method as the above.

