Proportion of subjects who reach 300 mg/day dose of AR101 by visit 16 will be analyzed using the Cochran-Mantel-Haenszel test adjusted by randomization stratification factors to assess the treatment difference in the proportion of subjects who reach the 300 mg/day dose of AR101 in the FAS. The proportion of subjects who reach the 300 mg/day dose of AR101 and its 95% confidence interval will be calculated for each treatment group with Clopper-Pearson confidence limits. Estimate of treatment difference, p-value, and the 2-sided 95% confidence interval using normal approximation will be provided.

Time-to-event Endpoint at visit 16

Time from randomization to the first time when subjects reach 300 mg/day dose of AR101 during the 28 to 40-week treatment period will be analyzed using the Cox proportional hazards model including treatment and randomization strata as factors. The hazards ratio, its 95% confidence interval and p-value will be reported. The Kaplan-Meier plots will be provided.

Continuous Endpoints at visit 22 and visit 25

Change in cumulative tolerated dose (log transformed) of peanut protein during a DBPCFC from baseline to visit 22 in subjects (continuously) treated with dupilumab plus AR101 vs placebo plus AR101, and change in cumulative tolerated dose (log transformed) of peanut protein during a DBPCFC from baseline to visit 22 in subjects (previously) treated with dupilumab plus AR101 (and re-randomized to placebo plus AR101) vs placebo plus AR101, will be assessed in a similar fashion as in visit 16 including missing data imputation and sensitivity analysis.

Percent change from baseline to visit 22 and visit 25 in peanut-specific IgE in subjects continuously treated with dupilumab + AR101 vs placebo + AR101 will be analyzed in a similar fashion as in visit 16.

Binary Endpoints at visit 22

Proportion of subjects (continuously) treated with dupilumab + AR101 vs placebo + AR10, and proportion of subjects (previously) treated with dupilumab + AR101 and re-randomized to placebo + AR101 vs placebo + AR101, who 'pass' a post-maintenance DBPCFC with 2044 mg cumulative peanut protein at visit 22 will be assessed the same way as for visit 16 including missing data imputation and sensitivity analysis.

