10. APPENDIX

10.1. Summary of Statistical Analyses

Efficacy Analysis:

| Endpoints | Analysis Population | Primary Statistical Method | Supportive/Sensitivity Statistical Method | Subgroup Analysis | Other Analyses |
|---|------------------------|---|---|----------------------|----------------------|
| Primary Endpoint | | | · | | · |
| Proportion of subjects treated with dupilumab plus AR101 vs placebo plus AR101 who "pass" a post up- dosing DBPCFC with 2044 mg (cumulative) peanut protein at visit 16 | mFAS, FAS | Cochran-Mantel-Haenszel test/ MI for missing due to COVID-19, otherwise missing data as non-responder | Cochran-Mantel- Haenszel test with available visit 16 DBPCFC data | Yes | Bar chart |
| Secondary Endpoint | | | | | |
| Change in cumulative tolerated dose (log transformed) of peanut protein during a DBPCFC from baseline to visit 16 | mFAS, FAS | ANCOVA model/ MI for missing due to COVID-19, otherwise missing data imputed by BOCF method | ANCOVA model with available visit 16 DBPCFC data; MI method; van Elteren test with LOCF method/with available visit 16 DBPCFC data for change in cumulative tolerated dose | Yes | Bar chart |
| Proportion of subjects treated with dupilumab plus AR101 vs placebo plus AR101 who reach 300 mg/day dose of AR101 by visit 16 | mFAS, FAS | Cochran-Mantel-Haenszel test | No | Yes | Bar chart |
| Time from randomization to the first- time subjects reach the 300 mg/day dose of AR101 during up-dosing treatment phase (up to visit 16) | mFAS, FAS | Kaplan-Meier estimates; Cox regression model | No | No | Kaplan-Meier plot |

CONFIDENTIAL

Page 63 of 86

| Endpoints | Analysis Population | Primary Statistical Method | Supportive/Sensitivity Statistical Method | Subgroup Analysis | Other Analyses |
|---|------------------------|---|--|----------------------|-------------------|
| Proportion of subjects (continuously) treated with dupilumab plus AR101 vs placebo plus AR101 who 'pass' a DBPCFC with 2044 mg (cumulative) peanut protein at visit 22 | FAS- maintenance | Cochran-Mantel-Haenszel test/ MI for missing due to COVID-19, otherwise missing data as non-responder | Cochran-Mantel- Haenszel test with available visit 22 DBPCFC data | Yes | Bar chart |

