| Change in the cumulative tolerated dose (log transformed) of peanut protein during a DBPCFC from baseline to visit 22 in subjects (continuously) treated with dupilumab plus AR101 vs placebo plus AR101 | FAS- maintenance | ANCOVA model/ MI for missing due to COVID-19, otherwise missing data imputed by BOCF method | ANCOVA model with available visit 22 DBPCFC data; MI method; van Elteren test with LOCF method/with available visit 22 DBPCFC data | Yes | Line plot |
| Proportion of subjects (previously) treated with dupilumab plus AR101 vs placebo plus AR101 who 'pass' a DBPCFC with 2044 mg (cumulative) peanut protein at visit 22 | FAS- maintenance | Cochran-Mantel-Haenszel test/ MI for missing due to COVID-19, otherwise missing data as non-responder | Cochran-Mantel- Haenszel test with available visit 22 DBPCFC data | Yes | Bar chart |
| Change in the cumulative tolerated dose (log transformed) of peanut protein during a DBPCFC from baseline to visit 22 in subjects (previously) treated with dupilumab plus AR101 vs placebo plus AR101 | FAS- maintenance | ANCOVA model/ MI for missing due to COVID-19, otherwise missing data imputed by BOCF method | ANCOVA model with available visit 22 DBPCFC data; MI method; van Elteren test with LOCF method/with available visit 22 DBPCFC data | Yes | Line plot |
| Percent change from baseline to visit 16 in peanut-specific IgE in subjects treated with dupilumab plus AR101 vs subjects treated with placebo plus AR101 | mFAS, FAS | Rank-based ANCOVA model, missing data imputed by MI method | ANCOVA model with LOCF method | No | Line plot |
| Percent change from baseline to visit 22 in peanut-specific IgE in subjects (continuously) treated with dupilumab plus AR101 vs subjects treated with placebo plus AR101 | FAS- maintenance | Rank-based ANCOVA model, missing data imputed by MI method | ANCOVA model with LOCF method | No | Line plot |

| Endpoints | Analysis Population | Primary Statistical Method | Supportive/Sensitivity Statistical Method | Subgroup Analysis | Other Analyses |
|--|------------------------|--|--|----------------------|-------------------|
| Percent change from baseline to visit 25 in peanut-specific IgE in subjects (continuously) treated with dupilumab plus AR101 vs subjects treated with placebo plus AR101 | FAS- maintenance | Rank-based ANCOVA model, missing data imputed by MI method | ANCOVA model with LOCF method | No | Line plot |

Safety Analyses:

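### The visit 22 imputation models leave out the child's own visit 16 challenge result: a small loss of precision, and possibly an overstated pass rate in each group

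*SAP*

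**What the plan says.** Four secondary endpoints rest on the visit 22 food challenge: pass rate and change in log cumulative tolerated dose, each for continuous and for previous dupilumab against placebo (SAP 4.5.2).

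- **Binary endpoints.** SAP 5.6.2 says they "will be assessed the same way as for visit 16 including missing data imputation and sensitivity analysis".
- **Continuous endpoints.** These "will be assessed in a similar fashion as in visit 16 including missing data imputation and sensitivity analysis".
- **Visit 16 binary model (SAP 5.6.1).** For challenges missed because of COVID-19, "the missing data will be imputed by multiple imputation (MI) method for 10 times utilizing available post up-dosing DBPCFC data at visit 16". The predictors follow: "The MI will utilize logistic regression method with treatment group and randomization stratification".
- **Visit 16 continuous model (SAP 5.6.2).** "The MI will utilize regression method with treatment group, randomization stratification, and baseline tolerated cumulative amount of peanut protein DBPCFC (log transformed").
- **Other missing results.** The summary table in SAP 10.1 gives "MI for missing due to COVID-19, otherwise missing data as non-responder" for pass/fail and "MI for missing due to COVID-19, otherwise missing data imputed by BOCF method" for tolerated dose. It adds no predictor for visit 22.
- **Analysis set.** "The FAS-maintenance is the primary analysis set for efficacy analyses at visit 22" (SAP 3.1). Entry to it requires 300 mg/day of AR101 for at least 2 weeks, not a pass at visit 16. The same condition makes a subject due for the visit 16 challenge (SAP 2.4).

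**The concern.** At visit 16 there is no earlier on-treatment challenge to use, so a model with treatment group and strata is a natural choice. At visit 22 there normally is one: the same eight-dose challenge to 2044 mg, taken 24 weeks before. One would expect it to be a strong predictor of the missing value, and the carried-over models do not contain it.

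Nothing else in the models stands in for it. The re-randomization stratum (300 mg/day reached, yes or no; SAP 2.1) is constant within FAS-maintenance. Screening tolerated dose has a narrow range: entry requires dose-limiting symptoms at or before the 100 mg step (Protocol 7.2.1), so at most 1 + 3 + 10 + 30 = 44 mg was tolerated.

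Two things are at stake. One is precision. The other is that the imputation assumes COVID missingness to be unrelated to outcome given group and stratum. If children who failed at visit 16 are COVID-missing more often, that assumption fails, and the visit 22 pass rate, which describes maintained desensitization, comes out too high. The binary sensitivity analysis (available visit 22 data) makes essentially the same assumption, so its agreement would not reassure.

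**Working it through.** **The plan's own figures.** None exist for visit 22. The documents' only power figure is 80% for visit 16 (52 against 104 subjects, 40% against 65%, two-sided 5% Fisher test). Exact enumeration gives 81.1%, so it is reproduced, and nothing below changes it.

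**Inputs.** The predictor lists and missing-data rules are those above. Everything else is assumed, for one group and stratum:

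- q = visit 16 pass rate
- a and b = probability of passing at visit 22 after a visit 16 pass or fail
- m_p and m_f = share of visit 16 passers and failers who are COVID-missing at visit 22

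**Step 1: what is imputed.** Without a visit 16 term, every missing result is drawn at the observed pass rate:

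r = [q(1 − m_p)a + (1 − q)(1 − m_f)b] / [q(1 − m_p) + (1 − q)(1 − m_f)]

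The true rate is P = qa + (1 − q)b. If m_p = m_f, then r = P. With q = 0.65:

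- a/b = 0.75/0.35: 0.4875 + 0.1225 = 0.61, for passers and failers alike
- a/b = 0.85/0.25: 0.5525 + 0.0875 = 0.64, for both

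In simulation (3,000 trials, 10 imputations each, 41 and 42 subjects per group, IgE and weight strata omitted, 20% missing), adding the visit 16 result gives about 0.74 for passers and 0.36 for failers in the first case, and 0.84 and 0.27 in the second.

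**Step 2: one group's pass rate.** The group estimate is r, so the bias is r − P. Example with q = 0.65, a/b = 0.85/0.25, m_p = 5%, m_f = 25%: r = (0.6175 × 0.85 + 0.2625 × 0.25) / 0.88 = 0.5905 / 0.88 = 0.671, against P = 0.640. The bias is 3.1 points. Over the range tried:

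| q | a/b | Bias at 5%/15% missing | Bias at 5%/25% missing |
|---|---|---|---|
| 0.50 | 0.75/0.35 | 1.1 | 2.4 |
| 0.50 | 0.85/0.25 | 1.7 | 3.5 |
| 0.50 | 0.90/0.15 | 2.1 | 4.4 |
| 0.65 | 0.75/0.35 | 1.0 | 2.1 |
| 0.65 | 0.85/0.25 | 1.5 | 3.1 |
| 0.65 | 0.90/0.15 | 1.9 | 3.9 |
| 0.80 | 0.75/0.35 | 0.7 | 1.4 |
| 0.80 | 0.85/0.25 | 1.0 | 2.1 |
| 0.80 | 0.90/0.15 | 1.3 | 2.6 |

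With equal missingness the bias is zero in every row.

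**Step 3: the between-group difference.** Take q = 0.75 against 0.55, a/b = 0.85/0.25 and 5%/25% missing in both groups.

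- True rates: 0.70 and 0.58, difference 0.120.
- Planned model: (0.7125 × 0.85 + 0.1875 × 0.25) / 0.90 = 0.725 and (0.5225 × 0.85 + 0.3375 × 0.25) / 0.86 = 0.615, difference 0.110.

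Both rates rise, by 2.5 and 3.5 points, so most of the error cancels and the difference falls by about 1 point. The simulation agrees: 0.110 with the planned model and 0.118 with visit 16 added.

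**Step 4: precision when missingness is unrelated to visit 16.** Simulated SD of the difference, planned model against visit 16 added:

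| a/b | 10% missing | 20% missing |
|---|---|---|
| 0.75/0.35 | 0.110 vs 0.109 | 0.122 vs 0.119 |
| 0.85/0.25 | 0.110 vs 0.108 | 0.119 vs 0.113 |

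Both models are unbiased here: 0.118 and 0.119 against a true 0.120 in the last cell, within a simulation error of 0.119/√3000 = 0.002.

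**The case against.** The strongest reply is that the plan already handles most of the feared mechanism. Imputation covers only challenges missed because of COVID-19. A family that declines because the child reacted at visit 16 has not given a COVID reason, so the result is scored as a non-response, or as baseline for tolerated dose. This stands. Bias needs COVID-coded absence that still depends on the visit 16 result. The −7/+30 day window for visit 22 (Protocol Table 4) should also keep COVID-missing challenges few.

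The stakes are also low. SAP 5.6.3 sets no formal hypothesis or multiplicity control for the maintenance phase, and Protocol 11.4.3.2 calls the visit 22 analyses descriptive. This stands too.

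It is also said that visit 16 data are not ignored altogether: SAP 10.1 lists a van Elteren test with LOCF for the visit 22 tolerated-dose endpoints, where the value carried forward can be the visit 16 challenge. That is right, but it is a sensitivity analysis for the continuous endpoints only.

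Finally, the phrase about available visit 16 challenge data, read literally at visit 22, might suggest that visit 16 results enter the model. It describes the outcome data used for the imputation, and the explicit predictor list has no visit 16 term. The wording does need clarifying.

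**Conclusion.** The omission is real and cheap to repair; its likely effect is small. Only COVID-missing visit 22 challenges are affected, and the identical pass probability holds within one treatment group and stratum. If COVID missingness is unrelated to the visit 16 result, there is no bias and only a modest loss of precision (at most 0.119 against 0.113 in the cases run). If failers are missing more often, each group's pass rate is overstated by roughly 1 to 4 points (0.7 to 4.4 over the range tried), and the difference moves about 1 point or less. The last figure assumes the same missingness pattern in both groups. All rates are assumed, because the documents give no visit 22 rates and no COVID-missing counts.

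Three stronger readings are tempting but not supported:

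- **That the comparison is tilted towards dupilumab.** In the worked case the shift is about 1 point and against dupilumab.
- **That adding visit 16 removes all bias.** It does so only where missingness depends on visit 16 alone, given group and strata.
- **That visit 25 needs the same change.** Only subjects who passed 444 mg at visit 22 are eligible for that challenge (SAP 2.4), so much of its missingness is by design, and the visit 25 pass rate is exploratory (SAP 4.5.3).

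**What to change.** In SAP 5.6.2, replace the cross-reference with explicit visit 22 models for COVID-missing challenges:

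- **Pass/fail:** logistic model with treatment group (the three maintenance groups), randomization strata and visit 16 pass/fail.
- **Tolerated dose:** regression model with the same terms, screening log tolerated dose, and visit 16 log cumulative tolerated dose.
- **Order:** where visit 16 is also COVID-missing, impute visit 16 first and then visit 22 within each imputed data set. SAP 5.6.2 already imputes other repeatedly measured endpoints visit by visit.
- **Wording:** state that the models are fitted to available visit 22 challenge data, with visit 16 as a predictor.

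Leave the rules for non-COVID missing results and the visit 25 analyses as they are. The cost is SAP text and slightly more programming. No new data or visits are needed, and no sample size or power figure changes. The change should be made before the database is locked.

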5.6.3. Adjustment for Multiple Comparison

The overall Type-1 error rate of 0.05 (2-sided) will be controlled for the primary endpoint and the first secondary endpoint (i.e., change in the cumulative tolerated dose [log transformed] of peanut protein during a DBPCFC from baseline to visit 16) using a hierarchical testing procedure. Inferential conclusions about the first secondary endpoint require statistical significance at the 2-sided 0.05 significance level of the primary endpoint.

No formal hypothesis and adjustment for multiplicity will be undertaken for the maintenance phase.

5.6.4. Analysis of Exploratory Efficacy Variables

The analysis of other efficacy variables will be the same as the primary analysis described in Section 5.6.1 and Section 5.6.2 with the following exceptions. The analysis on biomarker variables will be specified in Section 5.11. The analysis on the proportion of days with allergy symptoms based on eDiary data will be specified in Section 5.12.

5.6.5. Subgroup Analysis

Subgroup analysis for the primary endpoint and the following secondary endpoints will be performed on mFAS and FAS-maintenance. Subgroups have been defined in Section 3.6.

- Change in cumulative tolerated dose (log transformed) of peanut protein during a DBPCFC from baseline to visit 16 in subjects treated with dupilumab plus AR101 vs placebo plus AR101
- Proportion of subjects treated with dupilumab plus AR101 vs placebo plus AR101 who reach the 300 mg/day dose of AR101 by visit 16
- Proportion of subjects (continuously) treated with dupilumab plus AR101 vs placebo plus AR101 who "pass" a post maintenance DBPCFC with 2044 mg (cumulative) peanut protein at visit 22
- Change in the cumulative tolerated dose (log transformed) of peanut protein during a DBPCFC from baseline to visit 22 in subjects (continuously) treated with dupilumab plus AR101 vs placebo plus AR101
- Proportion of subject (previously) treated with dupilumab plus AR101 (and re-randomized to placebo plus AR101) vs placebo plus AR101 who "pass" a post maintenance DBPCFC with 2044 mg (cumulative) peanut protein at visit 22
- Change in the cumulative tolerated dose (log transformed) of peanut protein during a DBPCFC from baseline to visit 22 in subjects (previously) treated with dupilumab plus AR101 (and re-randomized to placebo plus AR101) vs placebo plus AR101

The analysis method for the subgroup will be the same as the primary analysis described in Section 5.6.1 and Section 5.6.2. Interactions between the subgroups and treatment groups will be tested using the logistic regression model for the binary endpoints and using the ANCOVA model for the continuous endpoints. The model will include randomization strata, treatment group, subgroup, treatment by randomization strata interaction and treatment by subgroup interaction as factors. P-values for interaction term will be reported.

Forest plots of above efficacy endpoints across subgroups will be generated.

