2. INVESTIGATION PLAN

2.1. Study Design and Randomization

This is a Phase 2, multicenter, randomized, double-blind, parallel-group, 2-arm study in subjects aged 6 to 17 years inclusive who are allergic to peanut. The study consists of a screening period of up to 16 weeks, a 28 to 40-week double-blind treatment period, a 24-week maintenance phase, and a 12-week post-treatment follow-up period. In protocol amendment 3 to accommodate COVID-19 restrictions, double-blind treatment period was extended from 28 weeks to up to 40 weeks. Subjects who attend optional visits between week 28 and week 40 will have increased duration of exposure to AR101 and dupilumab.

Approximately 156 subjects will be randomized at baseline in a 2:1 ratio into one of 2 treatment arms (n=104 to dupilumab and 52 to placebo, in combination with up-dosing of AR101) according to a central randomization scheme provided by an IWRS. Randomization will be stratified by screening peanut-specific IgE level ($\leq 100 \text{ kUA/L}$ or $\geq 100 \text{ kUA/L}$) and body weight ($\leq 30 \text{ kg}, \geq 30 \text{ kg}$ and $\leq 60 \text{ kg}$, or $\geq 60 \text{ kg}$) at randomization. A minimum of 15 subjects for each weight group will be enrolled.

At visit 16 (or at the early termination visit for those who discontinue from study prior to visit 16), subjects previously in the dupilumab plus AR101 arm will be re-randomized in a 1:1 ratio into one of 2 treatment arms (dupilumab versus placebo, in combination with AR101), according to a central randomization scheme provided by IWRS. Randomization will be stratified by whether subjects achieve 300 mg/day AR101 for at least 2 weeks by visit 16 (Yes or No).

Subjects previously in the placebo plus AR101 arm will continue their treatment of placebo plus AR101 in the maintenance phase if they achieve 300 mg/day AR101 for at least 2 weeks at visit 16.

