3.6. Subgroups

Subgroups are defined by key baseline factors recorded on the eCRF (unless otherwise specified) and listed as the follows.

Subgroups to be considered for both efficacy and safety analyses:

- Age group (>=6 to <12 years, >=12 to <=17 years)
- Sex (Male, Female)
- Baseline weight group ($\leq 30 \text{ kg}, \geq 30 \leq 60 \text{ kg}, \geq 60 \text{ kg}$)
- Screening peanut-specific IgE level ($\leq 100 \text{ kUA/L or } > 100 \text{ kUA/L}$)
- Asthma and non-asthma history for primary and key secondary efficacy endpoint only
- AD and non-AD history for primary and key secondary efficacy endpoint only

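### SAP 5.6.5: for weight group and peanut IgE, which are themselves the randomization factors, the treatment-by-subgroup term adds 0 degrees of freedom when subgroup and stratum values agree

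*SAP*

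**What the plan says.** SAP 5.6.5 tests subgroup interactions by logistic regression for binary endpoints and by ANCOVA for continuous ones, always with the same terms: "The model will include randomization strata, treatment group, subgroup, treatment by randomization strata interaction and treatment by subgroup interaction as factors". It then commits to an output: "P-values for interaction term will be reported". The section covers seven endpoints: the primary, the first secondary, reaching 300 mg/day by visit 16, and four visit 22 endpoints. Neither 5.6.5 nor the summary table in 10.1 exempts any subgroup from the model.

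SAP 3.6 lists age group, sex, weight group and screening peanut IgE. It adds two with a narrower scope: "Asthma and non-asthma history for primary and key secondary efficacy endpoint only", and atopic dermatitis history with the same limit. On the source of the values it says: "Subgroups are defined by key baseline factors recorded on the eCRF (unless otherwise specified".

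Weight group and peanut IgE are also the stratification factors. SAP 2.1 says "Randomization will be stratified by screening peanut-specific IgE level" and goes on to name body weight. SAP 5.6.1 has the primary test "adjusted by randomization stratification factors (screening peanut-specific IgE level" and again adds weight. The cut-points are the same in both roles: 100 kUA/L for IgE, 30 and 60 kg for weight.

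The visit 16 re-randomization of the dupilumab arm uses a different stratifier: "Randomization will be stratified by whether subjects achieve 300 mg/day AR101 for at least 2 weeks by visit 16 (Yes or No". The visit 22 analysis set, FAS-maintenance, "is a subset of FAS and includes subjects in the FAS who achieve 300 mg/day AR101 for at least 2 weeks".

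**The concern.** A model that already lets the treatment effect vary across the strata has nothing left for a treatment-by-weight or treatment-by-IgE term to explain, because those two variables define the strata. Read literally, the SAP promises a p-value for a term that is empty.

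The two subgroups concerned are of particular interest. Weight group is the only subgroup that the protocol names (Synopsis and 11.4.3.1), and it determines the dupilumab dose. The background in protocol 3.2.1 describes lower tolerance of the highest challenge doses above the same IgE cut. At stake is whether the interaction tests for these two are pre-specified, or depend on a coding choice made in programming.

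**Working it through.** The SAP states no degrees of freedom for these tests, so it has no figure of its own to reproduce. The check is on the design matrix.

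**Inputs.** Treatment T, 2 arms. Strata: 2 IgE levels × 3 weight groups = 6 cells (SAP 2.1). Subgroups: weight, 3 levels, and IgE, 2 levels, with the same cut-points (SAP 3.6). Model terms from SAP 5.6.5. The illustration uses the 122 subjects of SAP 2.3, split 81/41 (assumed, about 2:1), with all 12 arm-by-stratum cells occupied.

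**Step 1: the algebra.** Write S(j,k) for the indicator of weight group j and IgE level k. When values agree, the weight indicator is W(j) = S(j,low) + S(j,high). Multiplying by T gives T·W(j) = T·S(j,low) + T·S(j,high). Both right-hand columns are already in the treatment-by-strata term, so T·W(j) adds nothing. The same holds for IgE, summing over weight. This does not depend on cell sizes.

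**Step 2: ranks under the SAP's model.**

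- Six-level strata: 1 + 1 + 5 + 5 = 12. After adding the weight terms (16 columns) the rank is 12; after adding the IgE terms (14 columns) it is 12. Added: 0 df.
- Two-factor strata: 1 + 1 + (2 + 1) + (2 + 1) = 8. After adding the duplicate weight terms (12 columns) or IgE terms (10 columns) it is 8. Added: 0 df.

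In an illustrative logistic fit the deviance change was 0.0 for both subgroups. The codings differ in what remains. With two factors, treatment-by-weight and treatment-by-IgE are already present as the strata interactions, and only the repeat is empty. With six levels, treatment-by-strata is a single 5 df term that tests neither factor alone.

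**Step 3: if eCRF and IWRS values differ.** SAP 3.6 takes subgroups from the eCRF, while 5.6.5 does not state the source of the model strata. Let D(j) be the eCRF weight indicator minus the stratum-derived one. It is non-zero only for discordant subjects. Given the strata terms, adding T·W(j) is the same as adding T·D(j). If all discordant subjects are in one arm, T·D(j) equals D(j) or zero, and the interaction still has 0 df. Any df that does appear comes from discordant subjects alone, so the p-value does not test effect modification by weight or IgE. The documents give no count of such subjects.

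**Step 4: visit 22.** If the day 1 strata are meant, Steps 1 to 3 apply unchanged. If the re-randomization stratifier is meant, it is constant in FAS-maintenance. Adding T·weight then takes the rank from 4 to 6 (2 df), and adding T·IgE takes it from 3 to 4 (1 df), so both can be tested.

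**Step 5: number of tests.** Reading the key secondary endpoint of SAP 3.6 as the first secondary endpoint, two endpoints have 6 subgroups and five have 4: 2×6 + 5×4 = 32 tests. Affected at visit 16: 3 endpoints × 2 subgroups = 6. Affected at visit 22 on the day 1 reading: 4 × 2 = 8, for a total of 14. On the other reading the total stays at 6.

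**Step 6: the repaired model.** Intercept, T, weight and IgE: 1 + 1 + 2 + 1 = 5. Adding T·weight gives 7 (2 df); adding T·IgE gives 6 (1 df). If treatment by the other factor is kept, the ranks go from 6 to 8 for weight and from 7 to 8 for IgE, with the same df.

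**The case against.** The strongest reply is that two-factor coding is the natural reading. SAP 5.6.1, 5.6.2 and 5.11 all speak of stratification factors or variables, in the plural. On that reading the interaction of interest is in the model, and the gap is only an unstated instruction to drop a duplicate. Software that merges duplicate terms, or a sequential test with the subgroup term entered first, would also return 2 df or 1 df. A 0 df line is visible in the output, and a programmer would meet it on the first run. The protocol promises subgroup analyses but no interaction tests.

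Much of this stands. A reader might infer that the plan can yield no interaction test for weight or IgE under any reading. The documents do not support that: the 0 df result needs agreeing values, and under two-factor coding the test survives as a strata interaction. A reader might also take all 14 tests as affected. Eight of them depend on which strata apply at visit 22. SAP 5.6.2 handles visit 22 in the same way as visit 16, which favors the day 1 strata, but 5.6.5 does not say so.

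What does not stand is that nothing needs writing. SAP 5.6.5 speaks of strata without fixing the coding, the deletion or a sequential order, and it lists treatment-by-strata before treatment-by-subgroup. The discordant case is also not self-revealing: it prints an ordinary-looking p-value.

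**Conclusion.** The point holds and is minor. As listed, the treatment-by-subgroup term for weight group and for peanut IgE adds 0 df when subgroup and stratum values agree, under either coding. Where they disagree, it tests something else. Six visit 16 tests are affected: two each for the primary, first secondary and 300 mg/day endpoints. Eight visit 22 tests are affected only if the day 1 strata apply there.

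A reader might go further and doubt the subgroup results or the primary analysis. The documents give no ground for that. These p-values are outside the hierarchy in SAP 5.6.3, and the primary result, within-subgroup estimates and forest plots do not use this model. The age, sex, asthma and atopic dermatitis interactions each keep 1 df by rank.

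The conclusions concern rank only. Whether the logistic fits converge with sparse cells is a separate question and is not claimed here.

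The 300 mg/day endpoint carries a further limit. SAP 5.6.5 runs the visit 16 subgroup tests on the mFAS. SAP 3.1 restricts that set to subjects who had the visit 16 challenge, and SAP 2.4 and 4.5.1 give the challenge only to those who reached 300 mg/day for at least 2 weeks. Every subject is then a responder, and no logistic interaction can be estimated for any subgroup. Only under the definition in protocol 11.3.1, which adds early discontinuers, do the two tests for this endpoint become repairable.

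**What to change.** Add to SAP 5.6.5:

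> When the subgroup is weight group or peanut IgE level, weight group and IgE level are entered once each as two separate factors from a single source, the interaction tested is treatment by that factor, and the six-level or duplicate treatment-by-strata term is omitted (treatment by the other stratification factor may be kept). For visit 22 endpoints, randomization strata are those of the day 1 randomization.

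The eCRF is the natural single source, since SAP 3.6 already uses it for the subgroups. Whether to keep treatment by the other factor should be settled before database lock. Dropping it means that each test no longer adjusts for effect modification by the other factor; keeping it stays closer to the present model at the cost of 1 or 2 further parameters.

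For the 300 mg/day endpoint, the mFAS definitions in SAP 3.1 and protocol 11.3.1 must also be reconciled, or the interaction tests for that endpoint dropped.

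The cost of the main change is two sentences, with no new data and no effect on any confirmatory test.
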